6.4 Identification of Severe Exacerbations (SE)

1. Filter the medication data (MEDS) to keep all courses of oral corticosteroids (CLASS3=OCS) and other medications that are intravenous uses of the same medications - identify those by looking for CLASS3='Other Specify' and lowercase(CLSSP) with values: 'intravenous corticosteriod' 'intravenous corticosteroid' 'cortcosteroid iv' 'corticosteroid iv'. Note there are spelling mistakes in the entered data.
2. Merge the medication data with the AE data by patient and AE related number (RELAENO) on the medication data with AENUM on the AE data.
3. Use the onset date and the resolution date of the AE to determine the length of the SE. If an AE has no resolution date, impute the date of the most recent follow-up (scheduled or

Study Reference Number E7080

unscheduled) as the resolution date. For partial onset and resolution dates, impute dates as described in Section 6.3.

4. When an AE matches with a course of medication, the AE is considered to be an SE, however, when AEs that are SEs occur too close together, the combined AEs are one SE. If the resolution date of one AE selected as an SE is \leq 6 days before the onset date of another AE that is an SE, then combine the AEs into one SE. There could be more than two AE combined into a single SE.
5. SEs are classified in the time period where the onset date of the SE occurs regardless of the duration of the SE.
6. For each time period, count the number of SEs for each patient and whether the patient has an SE or not. Two types of summaries will be done for the SEs (also ER visits and hospitalization) to include the following patients: (1) patients with the follow-up visit or later visit for that time period, and (2) patients from (1) and patients with any SE in the time period.

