6.7 Data collection and Follow-up schedule

The planned study visits are outlined in the Study Flow Chart shown in Figure 2.

All data will be collected using appropriately designed case report forms (CRFs/eCRFs). Information on adverse events, incidences of OCS pulses for worsening of asthma symptoms, emergency room visits for respiratory symptoms, and hospitalizations for respiratory symptoms will be actively solicited by an appropriately qualified member of the clinical study site team during quarterly telephone contacts or at time of in-office visits.

Daily diaries will not be used in this clinical study, and all information solicited from the study subjects will be based on recall since the last contact (maximum recall time of 3 months). Episodes of worsening of asthma symptoms requiring treatment with oral corticosteroids, emergency room visits and hospitalizations for respiratory symptoms are rare events and are readily recalled for immediate past periods of 3 month duration. This approach will be consistent with data collection methodology in the AIR2 Trial.

The following data will be collected at the specified visits/evaluations:

Enrollment

- Medical history (including maintenance asthma medications and history of respiratory infections)
- Occurrence of events in the 12 month period prior to study enrollment
 - Severe exacerbations (pulses of systemic corticosteroids (tablets, suspension, or injection) for asthma symptoms)
 - Emergency room visits for asthma symptoms
 - Hospitalizations for asthma symptoms
- Forced Expiratory Volume in 1 second: FEV₁ (pre- and post-bronchodilator)
- Physical examination (including body weight)
- Chest X-ray (Lateral and PA)
- Asthma Quality of Life Questionnaire (AQLQ)

Treatment Period (Day of 1st bronchoscopy till 6 weeks after 3rd/last bronchoscopy)

- Adverse events
- Emergency room visits for respiratory symptoms
- Hospitalizations for respiratory symptoms
- FEV₁ (pre- and post-bronchodilator)

Phone Contact at every 3 Months between Annual Visits

- Adverse events
- Severe exacerbations
- Maintenance asthma medications
- Emergency room visits for respiratory symptoms
- Hospitalizations for respiratory symptoms

Annual Visits at 1, 2, 3, 4 and 5 years from end of Treatment Period (6 week visit following 3rd/last bronchoscopy)

- Adverse Events
- Severe exacerbations
- Physical examination (including body weight)
- Maintenance asthma medications

- Emergency room visits for respiratory symptoms

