- Hospitalizations for respiratory symptoms
- FEV₁ (pre- and post-bronchodilator)

All adverse events will be actively solicited by an appropriately qualified member of the clinical study site team at the time of follow-up evaluations. For the periods between scheduled study visits or telephone contacts, subjects will be encouraged to keep track of any adverse events, pulses of oral corticosteroids for worsening of asthma symptoms, emergency room visits for respiratory symptoms or hospitalizations for respiratory symptoms in a medical event log. Subjects will be trained to contact study site team in the event there is an emergency room visit or hospitalization due to respiratory symptoms.

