2 ENDPOINT ANALYSIS

2.1 Primary Endpoint

The primary endpoint will be the proportion of subjects experiencing severe exacerbations during the subsequent 12-month period (for Years 2, 3, 4, and 5) compared to the first 12-month period after the Alair treatment.

Note: Severe exacerbation is defined as worsening of asthma symptoms requiring use of systemic corticosteroids (tablets, suspension, or injection). For subjects already taking oral corticosteroids on a daily or alternate day basis, a severe exacerbation will be defined as a worsening of asthma symptoms requiring any increase in daily dose of systemic corticosteroids. For consistency, courses of corticosteroids separated by 1 week or more will be treated as separate severe exacerbations.

The primary statistical objective is to demonstrate that the proportion of subjects who experience severe exacerbations in the subsequent 12-month follow-up (for Year 2, Year 3, Year 4 and Year 5 [in 12-month periods]) is not statistically worse when compared with the proportion of the first 12-months, which begins 6 weeks after the last Alair treatment. This objective will be met if the upper 95% confidence limit of the difference in proportions (i.e., the subsequent 12-month proportion minus the first 12-month proportion) is less than 20%.

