2.1.3 Statistical Methods

See Section 6.4 for how to identify severe exacerbations.

The proportions of patients with severe exacerbations at each year (p_k , $k=1$ to 5) will be calculated in two ways:

1. Complete Follow-up: using patients who complete the annual follow-up visit or have a follow-up visit (office or phone call) after the visit for that particular year if the annual visit is missed.
2. Complete/Partial Follow-up: using patients who complete the annual follow-up visit no earlier than the start of the follow-up window, have a follow-up visit (office or phone call) after the visit for that particular year if the annual visit is missed, have sufficient follow-up for the year, or had a severe exacerbation during the time period regardless of the amount of follow-up. Sufficient follow-up is having any follow-up visit (office or phone call), adverse event onset date, or hospitalization date that gives the patient at least the number of days of follow-up after the last BT procedure + 42 days given in Table 2.

Table 2. Days for sufficient follow-up by follow-up time

Study Reference Number E7080

Time	Days for sufficient follow-up after the follow-up period starts*
1 Year	337 days
2 Years	702 days
3 Years	1067 days
4 Years	1432 days
5 Years	1797 days

* - the follow-up period starts at last BT procedure + 42 days. The number of days in this column represents the start of the follow-up window after the follow-up period starts and is calculated as # years times 365 days minus 28 days.

All analyses will be done for patients with Complete and Complete/Partial Follow-up. Point estimates and 95% confidence intervals for the proportion of subjects experiencing severe exacerbations during each of the 12-month evaluation periods will be provided. Additionally, the exact upper 95% confidence limit for the difference between the subsequent 12-month proportions and the first 12-month proportion will be calculated, based on methods assuming paired samples; in this analysis, each subsequent 12-month proportion would represent comparisons between the first-year proportion and the second-, third-, fourth-, and fifth-year proportions.

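### SAP 6.4, the program that derives the primary endpoint, does not carry out the severe-exacerbation definition in SAP 2.1 on route, asthma worsening or dose increase, and does not say whether the CRF does so.

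*SAP*

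**What the plan says.** SAP 2.1 defines a severe exacerbation as "worsening of asthma symptoms requiring use of systemic corticosteroids (tablets, suspension, or injection"). For subjects already on daily or alternate-day oral steroids, it requires "worsening of asthma symptoms requiring any increase in daily dose of systemic corticosteroids". Protocol 5.6 and 8.1 give the same definition.

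SAP 2.1.3 then hands the derivation to the programming section: "See Section 6.4 for how to identify severe exacerbations". In SAP 6.4:

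- Step 1 says "Filter the medication data (MEDS) to keep all courses of oral corticosteroids (CLASS3=OCS) and other medications that are intravenous uses of the same medications". The intravenous records are found through four literal free-text values, two of them misspelled, and the SAP remarks that the entered data contain spelling mistakes.
- Step 2 joins these records to the adverse event (AE) data by patient and AE number.
- Step 4 says "When an AE matches with a course of medication, the AE is considered to be an SE".
- Steps 3, 5 and 6 deal with dates, assignment to a time period and counting.

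On data capture, Protocol 6.7 says that sites actively solicit "incidences of OCS pulses for worsening of asthma symptoms", and that subjects are encouraged to log "pulses of oral corticosteroids for worsening of asthma symptoms". The enrollment history item is "Severe exacerbations (pulses of systemic corticosteroids (tablets, suspension, or injection) for asthma symptoms"). Protocol 6.7 also lists severe exacerbations as an item collected at every quarterly call and annual visit. SAP 6.4 does not mention that item.

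**The concern.** This is the only endpoint with a hypothesis test; SAP 2.2.1 states that the secondary endpoints have none. A programmer who follows 6.4 literally could count subjects who do not meet the definition and miss some who do.

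The test compares each later year with Year 1 against a 20-point margin. Over-counting at the same rate in every year shrinks the difference between years, which makes non-inferiority easier to declare. Error that changes over time can push the result either way. The planned tipping-point analysis (SAP 2.1.3) addresses patients with inadequate follow-up, so it would not show misclassification.

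**Working it through.** **Text comparison**

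| Element | SAP 2.1 | SAP 6.4 |
|---|---|---|
| Route | Tablets, suspension or injection | CLASS3=OCS, or Other Specify with one of four intravenous text values |
| Indication | Asthma symptoms worsen | Any AE linked to a kept course; no diagnosis or term filter |
| Maintenance OCS | Daily dose is increased | No step uses dose |

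Each row matters in this trial.

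- Route: an intramuscular injection, or an intravenous one worded differently, is not selected unless it was coded as OCS. The SAP is dated 27 June 2016 and Protocol 16.0 projects completion in December 2019, so wording entered later is not covered.
- Indication: the AE definition in Protocol 8.0 covers any illness.
- Dose: inclusion criterion 3b admits subjects on up to 10 mg per day of oral steroid.

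**The plan's own figure**

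SAP Table 1 (Year 1 0.33, later year 0.41, margin 0.20, n 250 and 200, one-sided 0.05):

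- SE = √(0.33×0.67/250 + 0.41×0.59/200) = 0.0458
- Power = Φ((0.20 − 0.08)/0.0458 − 1.645) = 83.6%, against 83% stated

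The table reproduces. At one-sided 0.025 the same row would give 74.6%, so 0.05 is the level used.

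**Illustration of an over-count**

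The documents give no error rates, so these are assumed. Let r be the number of non-asthma, steroid-linked AEs per subject-year (Poisson, independent between years).

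- Observed proportion = 1 − (1 − p)e^(−r)
- With equal r, observed difference = (true difference) × e^(−r)

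The true proportions are 0.33 and 0.53, exactly at the margin, with 200 pairs and an assumed between-year correlation of 0.2. SAP 2.1.3 calls for an exact paired limit but names no method. The paired (Nam) score test at one-sided 5% stands in for it, evaluated by enumerating the discordant pairs, for one year's comparison.

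| r in Year 1 | r in Year k | Observed Year 1 | Observed Year k | Difference (points) | False success |
|---|---|---|---|---|---|
| 0 | 0 | 33.0% | 53.0% | 20.0 | 5.0% |
| 0.02 | 0.02 | 34.3% | 53.9% | 19.6 | 6.0% |
| 0.05 | 0.05 | 36.3% | 55.3% | 19.0 | 7.8% |
| 0.10 | 0.10 | 39.4% | 57.5% | 18.1 | 11.2% |
| 0.05 | 0.07 | 36.3% | 56.2% | 19.9 | 5.3% |
| 0.05 | 0.08 | 36.3% | 56.6% | 20.3 | 4.3% |

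With correlation 0 or 0.4, the r = 0.10 row gives 10.5% or 12.0%.

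At a true 8-point difference (0.33 and 0.41) with equal r of 0.02, 0.05 or 0.10, the observed difference is 7.8, 7.6 or 7.2 points. The chance of success moves from 87.4% to 87.5%, 87.7% or 88.2%.

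**Other two gaps, same test, correlation 0.2**

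- Maintenance OCS: if a share s of all subjects is falsely counted every year, the difference becomes 20 × (1 − s). For s of 0.5% to 2.5% it is 19.9 to 19.5 points, and false success is 5.3% to 6.3%.
- Missed courses: losing 5-10% of exacerbations at random gives 5.0% to 6.6%. The effect is small because a subject with several events in a year is still counted if one is missed.

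**The case against.** The strongest reply is that MEDS, CLASS3 and RELAENO are database fields, and whether 6.4 falls short of 2.1 depends on a CRF that we do not have. Much in the documents supports that reply:

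- Protocol 6.7 directs sites and subjects to steroid courses given for asthma worsening, so data entry may already apply part of the asthma test.
- Stable maintenance steroid has no evident reason to carry an AE number, so the AE link in step 2 is a partial proxy for a dose increase.
- The four intravenous values look as if they were taken from the data already entered.

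These points stand, and they limit the conclusion to a mismatch in specification. They do not remove it. Neither document says that these fields enforce asthma worsening, that other injections are coded as OCS, or that a dose increase is entered as its own course. Protocol 7.3.4 has prophylactic antibiotics recorded on the Medication Log, so that log is not confined to asthma drugs. This does not show that steroids for other illnesses are recorded there and linked to AEs.

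A reader might make three stronger inferences that the documents do not support:

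- **On-study capture is oral-only.** Two prompts do name only oral courses. But Protocol 6.7 also collects severe exacerbations at each quarterly and annual contact, and Protocol 5.6 and 8.1 define that term to include injection.
- **Peri-procedural prednisone is counted.** Protocol 7.3.4 keeps it off the concomitant medications.
- **The error favours success.** That requires an over-count that is about equal across years. In the table, a rise from 0.05 to 0.07 or 0.08 removes or reverses the effect.

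**Conclusion.** The mismatch between SAP 6.4 and SAP 2.1 is certain on the text: 6.4 states a narrower route, no asthma test and no dose test. That is a stated rule that departs from the definition it is meant to apply, and it governs the only tested endpoint.

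Its effect on the result is not known. The range of about 6-11% false success, against 5%, rests on assumed rates, equal error in all years, a true worsening exactly at the margin, 200 pairs and a correlation of 0.2. If all four years must pass, the overall false-success rate cannot exceed the single-year rate. A reader might infer that the endpoint is materially biased. The documents do not show this, since they give neither error counts nor the CRF. The case for acting is that the mismatch is cheap to remove before analysis, and no planned analysis would reveal it afterwards.

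**What to change.** Amend SAP 6.4 before analysis, as SAP 4.7 allows:

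1. **Step 1:** select all systemic corticosteroid records, oral and any injection, by drug and route. Review all Other Specify steroid records before database lock.
2. **Step 4:** require that the diagnosis or symptoms recorded on the linked AE show worsening of asthma, by one rule applied to all years. Protocol 8.0 already requires both fields on the AE form.
3. **Maintenance OCS subjects:** apply the dose-increase condition already in SAP 2.1.
4. **Where a CRF field already enforces one of these tests,** name that field in 6.4 instead.
5. **If severe exacerbation is a separate CRF item,** check the 6.4 output against it.

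The cost is an SAP amendment, some reprogramming and one review of free-text steroid records and linked AEs. No new data are needed if diagnosis, route and dose are already recorded. The sample size and Table 1 do not change.

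### SAP 6.4 separates severe exacerbations by adverse-event dates, although SAP 2.1 defines separation by corticosteroid courses, so the scored count can differ from the defined endpoint

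*SAP*

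**What the plan says.** SAP 2.1 gives the separation rule for the primary endpoint: "courses of corticosteroids separated by 1 week or more will be treated as separate severe exacerbations". Protocol 4.0, 5.6 and 8.1 carry the same rule.

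SAP 2.1.3 sends the primary analysis to SAP 6.4 for identifying SEs. The steps there are:

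- **Steps 1-2.** Steroid courses are taken from the medication data (MEDS) and linked to AEs by AE number.
- **Step 3.** "Use the onset date and the resolution date of the AE to determine the length of the SE". Open AEs get an imputed end: "If an AE has no resolution date, impute the date of the most recent follow-up (scheduled or" unscheduled). Partial dates are referred elsewhere: "For partial onset and resolution dates, impute dates as described in Section 6.3".
- **Step 4.** An AE that matches a course is an SE, and "when AEs that are SEs occur too close together, the combined AEs are one SE". Too close means that one AE resolves 6 days or less before the next begins.
- **Step 5.** "SEs are classified in the time period where the onset date of the SE occurs regardless of the duration of the SE".

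No step compares the start or stop dates of courses. The SAP revision history describes the algorithm as made more specific and declares no change of definition.

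**The concern.** The two sections use the same threshold (a 6-day gap joins, a 7-day gap separates) but apply it to different dates. An AE often outlasts the course given for it, so AEs can be close together while the courses are more than a week apart. Two separated courses linked to one AE are never compared at all.

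Two results are exposed. The SE rate, a secondary endpoint, loses every course that is absorbed. The yearly yes/no indicator behind p_k - p_1 can lose an event when the absorbed course falls in a later period than the SE's onset. The planned tipping-point analysis varies only missing outcomes, so it would show neither effect.

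Step 3 adds a separate risk. If the latest follow-up means last contact, and if overlapping AEs are merged, one unresolved steroid-linked AE could absorb all of a subject's later SEs. Step 4 is silent on overlap, and SAP 6.3 has rules for onset dates only.

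**Working it through.** **Both rules on constructed records.** Day 0 is the last procedure plus 42 days. Years are 365 days (SAP 4.6), so Year 2 starts at day 365.

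| Record | Gaps | SAP 2.1 | SAP 6.4 |
|---|---|---|---|
| AE 355-363, course 355-359; second AE and course from day 367 | courses 367-359 = 8; AEs 367-363 = 4 | 2 SEs: Years 1 and 2 | 1 SE: Year 1 |
| One AE 350-410, courses 350-355 and 400-405 | courses 400-355 = 45 | 2 SEs: Years 1 and 2 | 1 SE: Year 1 |
| One AE -20 to 65, courses -20 to -15 and 60-65 | courses 60+15 = 75 | 2 SEs: treatment period and Year 1 | 1 SE: treatment period |
| AE 100-105, course 100-110; AE and course 113-118 | courses 113-110 = 3; AEs 113-105 = 8 | 1 SE | 2 SEs |

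The first two records lose a Year 2 event, the third loses a Year 1 event, and the fourth overcounts. All have complete dates.

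**SE rate.** Let m be the share of SEs that hide a second separated course. The documents give no value; assume 5-10%. The undercount is m/(1+m): 0.05/1.05 = 4.8% and 0.10/1.10 = 9.1%. On the earlier trial's 0.48 per subject-year (Protocol 3.1), used for scale only, 0.48 becomes 0.457 or 0.436.

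**Yearly proportion.** Let g be the days between course starts (assumed 14-90). Expected crossings per boundary in 200 subjects are 200 × 0.48 × m × g/365. Multiply by 0.67 for subjects with no other SE that year (33% from SAP 2.1.2):

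- m = 0.05, g = 14: 0.18 crossings, 0.12 subjects, 0.06 points
- m = 0.10, g = 30: 0.79 crossings, 0.53 subjects, 0.26 points
- m = 0.10, g = 90: 2.37 crossings, 1.59 subjects, 0.79 points

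This treats SEs as unclustered. A gamma-Poisson simulation (1,000,000 subjects, mean 0.48, 33% per year, shape 1.14) gives smaller losses, about 0.04 to 0.55 points, nearly equal in every year. At m = 0.10, g = 30 each year loses about 0.18 points, so p_k - p_1 hardly moves. If the treatment-period SE rate is assumed to be doubled, Year 1 loses about 0.35-0.37 points and Year 2 about 0.17-0.19. The difference p_2 - p_1 then rises by about 0.18 points, against success.

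**Open AEs, under the last-contact and merge-overlaps readings only.** First, the plan's own test: power = Φ((0.20 - d)/SE - 1.645). With 33% vs 41% and 250 vs 200 subjects, SE = √(0.33×0.67/250 + 0.41×0.59/200) = 0.0458, and power = Φ(0.12/0.0458 - 1.645) = 83.6%. Table 1 states 83%, so the one-sided 5% test is confirmed.

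Now take 200 pairs at the margin (33% vs 53%) with between-year correlation φ. Then p11 = p1·p5 + φ√(p1(1-p1)p5(1-p5)). If a share q of all subjects has an open Year 1 AE that absorbs Year 5 events, d = 0.20 - q·p11/p1 and SE = √((p10 + p01 - d²)/200), with p10 raised by q·p11/p1.

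| φ | q | p11 | d | SE | False pass |
|---|---|---|---|---|---|
| 0 | 0.01 | 0.1749 | 0.195 | 0.0489 | 6.2% |
| 0 | 0.02 | 0.1749 | 0.189 | 0.0492 | 7.6% |
| 0.3 | 0.01 | 0.2453 | 0.193 | 0.0412 | 7.2% |
| 0.3 | 0.02 | 0.2453 | 0.185 | 0.0418 | 9.9% |

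With q = 0 it is 5.0%. At 33% vs 33% the pass probability is at least 99.5% with or without the imputation. Here q and φ are assumptions; q of 1-2% is 3-6% of Year 1 exacerbators.

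**The case against.** The strongest reply is that 6.4 is a fair way to put the definition into practice. The definition starts from a worsening of symptoms. The AE records that worsening, the course shows that steroids were needed, and the threshold is kept. Protocol 8.0 treats anything that appears or worsens as an AE, so a fresh worsening after recovery should become a new AE. That narrows the route of two courses under one AE but does not close it. It also leaves the first constructed record untouched, where two properly recorded AEs are merged. Nothing in the documents confirms that MEDS holds course dates, so AE dates may be all there is. If so, the SAP should say so.

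A second reply is that the primary result hardly moves. That stands for the main mismatch. The illustration also mixes sources: Protocol 3.1 pairs 0.48 per year with 26% of subjects, while 33% is a planning ceiling. The figures show scale only.

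A reader might infer that 6.4 tilts the test towards non-inferiority by losing later-year events. The documents do not support that. Year 1 can lose events to SEs begun in the treatment period, and Protocol 3.1 reports a transient rise in respiratory events in that phase of the earlier trial. The open-AE route could favour success, but it needs two readings that the SAP does not state. AE follow-up to resolution or stabilization, quarterly contacts and data queries also limit it.

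**Conclusion.** The mismatch is real and follows from the text alone: the rule that scores the endpoint does not apply the stated definition. It should be fixed before the analysis, but it does not show that the study's conclusion would change.

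The main consequence is an undercount of the descriptive SE rate of about 5-9%, if 5-10% of SEs hide a second separated course. For the yearly proportions, the loss needs a merged or multi-course SE that crosses a period boundary. It is a fraction of a percentage point per year under the assumed values of m and g, and its net direction on p_k - p_1 is not fixed. The open-AE effect could reach a false-pass rate of 6-10% at the margin, but only with 1-2% of subjects affected and both unstated readings adopted. Otherwise it is close to nil. The documents give no frequency for multi-course or open steroid-linked AEs, so confidence in the size is limited. Overlapping AEs and partial resolution dates are minor drafting gaps.

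**What to change.** Amend SAP 6.4 as follows.

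- Where MEDS holds course start and stop dates, apply the 1-week gap to them and assign each resulting SE to the period in which its first course starts.
- Do not merge SEs on an imputed resolution date.
- If course dates are not available, state in 2.1 and 6.4 that AE dates are a proxy. Report by period the number of steroid-linked AEs with more than one course record, and of open steroid-linked AEs.
- Report the primary result and the SE rate under course-based and AE-based counting where possible, and with and without the open-AE imputation.
- State whether overlapping AEs merge, and give a rule for partial resolution dates.

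Dating a later course by the contact that reported it is not a sound substitute. Protocol 6.7 solicits "incidences of OCS pulses for worsening of asthma symptoms" with a "maximum recall time of 3 months". That cannot check a 1-week gap, and the ±4-week annual visit window could turn a late pulse into a false event in the next year. Scoring an SE in every period in which a course starts should also be avoided, because one SE could then count in two years.

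The cost is an SAP amendment, which 4.7 allows before the analysis, some reprogramming of steps 3-5 and the sensitivity runs. The main limitation is reliance on course dates that the documents do not confirm.

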8.0 Adverse Events

Definition: An adverse event is any sign, symptom, illness, clinically significant abnormal laboratory value, or other adverse medical event that appears or worsens in a subject during a clinical study, regardless of whether or not it is considered related to the procedure used as part of the protocol.

- It is the responsibility of the Investigator to decide when an adverse event has occurred.
- Adverse event information will be collected throughout the study.
- Adverse events will be recorded on the Adverse Event CRF/eCRF by the Investigator or clinical study staff and must include
 - Diagnosis
 - Symptoms
 - Date of onset
 - Date of resolution
 - Severity
 - Relationship to the procedure
- All adverse events will be monitored until they are adequately resolved or stabilized with no further significant change expected.

All Serious Adverse Events or complications must be reported to Clinical Affairs at Asthmatx, Inc. within 3 working days via

Telephone: [name]

FAX: [name], or

E-mail: [contact]

For all Serious Adverse Events, reports relating to the subject's subsequent medical follow-up must be submitted to Sponsor until the event has subsided or, in case of permanent impairment, until the event stabilizes and the overall clinical outcome has been ascertained.

Asthmatx Clinical Affairs will perform real time data review to observe any unanticipated or unforeseen events and to monitor the actual rate of anticipated events. All events will be MedDRA coded and entered into a database for later analyses. This review will occur on an ongoing basis upon event notification.

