In the event that a hospital admission is for less than 24 hours, the incidence will be reported as a serious adverse event, but will not be counted as a hospitalization.

D. Unanticipated Adverse Device Effect (UADE): Any serious adverse effect on health or safety or any life-threatening problem or death caused by, or associated with, a device, if that effect, problem, or death was not previously identified in nature, severity, or degree of incidence in the investigational plan or application (including a supplementary plan or application), or any other unanticipated serious problem associated with a device that relates to the rights, safety, or welfare of Subjects (21 CFR 812).

All unanticipated adverse device effects must be submitted by the Investigator to the reviewing IRB and Sponsor within 10 working days (see Appendix B).

E. Adverse Event Relationship: The relationship of an Adverse Event to the procedure will be attributed using the following definitions:

1. **Not Related:** No evidence that the timing of the adverse event has a relationship to the procedure performed.
2. **Possibly Related:** The adverse event has a timely relationship to procedure performed. However, a potential alternative etiology may be responsible for the adverse event.
3. **Probably Related:** The adverse event has a timely relationship to study procedure performed and the causative relationship can clearly be established. No potential alternative etiology is apparent.

F. Adverse Event Status: The status of an adverse event shall be determined as per the following definitions:

1. **Resolved:** An adverse event which returns to baseline status.
2. **Resolved with residual effects:** An adverse event which is not expected to return to baseline status.

Residual effects should be documented in the subject's medical chart and on the Adverse Event CRF/eCRF.

3. **Continuing:** An adverse event which is expected to resolve back to baseline status at some point in the future.

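### SAP 6.4 sets no cap on the imputed end of an unresolved exacerbation AE, so on its natural reading one open AE can absorb later severe exacerbations and favour the durability claim

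*SAP*

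**What the plan says.** SAP 6.4 derives SEs in steps. Steroid courses are matched to AEs, and "When an AE matches with a course of medication, the AE is considered to be an SE". The AE's onset and resolution dates give the length of the SE. For a missing end, step 3 reads: "If an AE has no resolution date, impute the date of the most recent follow-up", scheduled or unscheduled. No maximum duration is given.

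Step 4 merges SE-linked AEs when one resolves no more than "6 days before the onset date of another AE that is an SE, then combine the AEs into one SE", and adds: "There could be more than two AE combined into a single SE". Step 5 then assigns the result: "SEs are classified in the time period where the onset date of the SE occurs regardless of the duration of the SE".

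The definition these steps should implement is in SAP 2.1 (also Protocol 4.0, 5.6 and 8.1 A): "courses of corticosteroids separated by 1 week or more will be treated as separate severe exacerbations".

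The protocol foresees AEs without a resolution date. Section 8.0 says: "All adverse events will be monitored until they are adequately resolved or stabilized with no further significant change expected". Section 8.1 F defines the status Continuing: "An adverse event which is expected to resolve back to baseline status at some point in the future".

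**The concern.** The imputed end date can lie years after the steroid course that made the AE an SE. Any later SE-linked AE that starts before that date, or within 6 days after it, meets the merge rule if overlap counts. This happens even when the site recorded each exacerbation as its own AE with its own course.

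The loss is asymmetric. An AE left open in Years 1 to k-1 removes Year k failures and leaves its own year's failure in place, so p_k - p_1 falls. Exposure builds with time and is greatest for Year 5, the year on which the sample size rests. An AE left open from the Treatment Period also removes Year 1 events. That shrinks the difference toward zero, which at the margin again favours success. An AE that opens in Year k or later does not affect the Year k comparison.

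The annual SE rate, a secondary endpoint, is undercounted in the same way. The tipping-point analysis (SAP 2.1.3, 6.3) varies only subjects with missing data, whereas an absorbed subject counts as observed and event-free.

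**Working it through.** **1. The plan's own figure.** SAP Table 1 gives 83% power for 0.33 against 0.41, with 250 and 200 subjects, one-sided alpha 0.05 and margin 0.20. Power = Φ((0.20 − 0.08)/√(0.33×0.67/250 + 0.41×0.59/200) − 1.645) = Φ(0.12/0.0458 − 1.645) = 83.6%. The full row recomputes to 99.8, 99.5, 99.1, 98.3, 97.1, 95.1, 92.4, 88.5 and 83.6%, in agreement with the table. The test itself is understood correctly.

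**2. Steps 3-5 applied to one record.** Steroid-linked AEs start on days 200, 500, 900, 1300 and 1700 after the start of follow-up, one in each 365-day year. Last contact is day 1825.

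| Reading | SEs counted |
|---|---|
| First AE open, ended at last contact, overlaps merged | 1 (Year 1 only) |
| First AE closed on day 212 | 5 (one in each of Years 1-5) |
| First AE open, only gaps of 0 to 6 days merged | 5 |

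A parallel record with the first AE starting on day 100 and ended at the next 3-monthly contact (day 182) also keeps all five. The onsets here are at least 300 days apart, so SAP 2.1 calls for five.

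**3. Size at the margin.** From the documents: 200 pairs, Year 1 proportion 0.33, margin 0.20, one-sided 5%. Assumed: true Year 5 proportion 0.53 with a linear rise between; each SE-linked AE lacks a resolution date with probability q; closed AEs last about 10 days; last-contact reading with overlaps merged. Yearly event rate: λ = −ln(1−p) with no between-subject variation, or λ = s[(1−p)^(−1/s) − 1] with gamma frailty of shape s. For p = 0.33 this gives 0.40 (none), 0.49 (s = 1) and 0.61 (s = 0.5). For p = 0.53 it gives 0.76, 1.13 and 1.76.

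The trial passes if d + 1.645·√{[(b+c)/n − d²]/n} < 0.20, where d = (b−c)/n, b is the number of pairs failing in Year 5 only and c the number failing in Year 1 only. This is a large-sample limit; the SAP specifies an exact one.

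False-pass rate when the true difference is 20 points (small ranges reflect separate runs):

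| q | No variation | Shape 1 | Shape 0.5 |
|---|---|---|---|
| 0 | about 5% | about 5% | about 5% |
| 1% | 7-9% | 11-13% | 20% |
| 2% | 12-13% | 24-25% | 46% |
| 5% | 27-30% | 67-69% | 92% |

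The mean observed difference falls from 20 points to about 17-19, 14-18 and 7-15 points at 1%, 2% and 5%. Observed p_1 stays at about 0.33.

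**4. Other cases.** With no true change, frailty of shape 1 to 0.5 gives an apparent difference of −1.0 to −1.6, −2.1 to −3.2 and −4.9 to −7.0 points at 1%, 2% and 5% open. At the planning case of 0.33 against 0.41 (shape 1), the pass rate rises from 88% to 95% at 2% and to nearly 100% at 5%. If the imputed date is the next 3-monthly contact, the false-pass rate is 4.5-6.1% even with 10% open.

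**The case against.** The strongest reply is that the text does not force this result. An imputed end after the next onset is not, strictly, a date before it; if only gaps of 0 to 6 days merge, nothing is absorbed. Nor does the SAP define the most recent follow-up as the last contact in the database. Both points stand as limits. Merging overlaps is still the more natural reading of a rule about AEs too close together, and a programmer following the text would probably do it.

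Second, open AEs should be uncommon. Protocol 8.0 requires a resolution date on the AE record, 8.1 F offers a closing status for events with residual effects, contacts are every 3 months, and sites are queried and monitored. Absorption also needs a steroid-linked AE that is never closed while the site opens new ones for the same subject. At the margin, 5% open means about 39 to 56 such AEs among 200 subjects (shapes 1 and 0.5), which is a lot. These controls reduce the number but do not make it zero, and step 3 itself provides for such AEs.

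Third, the size depends on assumed variation between subjects. That also stands, although no variation at all is probably too favourable. Protocol 3.1 reports 0.48 exacerbations per subject-year and 26% of subjects affected in the earlier pivotal trial. A Poisson model over its 46-week period would give 1 − exp(−0.48×46/52) = 35%. That trial had a different population, and Protocol 4.0 notes that its exacerbation definition differed.

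**Conclusion.** The defect holds, conditionally. If the imputed end is the last contact and overlaps merge, one open steroid-linked AE erases all later SEs, contrary to the 1-week rule in SAP 2.1, and the error favours durability. With 1% / 2% / 5% of SE-linked AEs open, the false-pass rate at the margin is about 7-20% / 12-46% / 27-92% against about 5% nominal, from no between-subject variation to gamma frailty of shape 0.5. The open share, the event model and the large-sample limit are assumptions.

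A reader might infer that the primary analysis is shown to be biased toward success, or that every open AE absorbs later events. The documents support neither. They give no frequency of open SE-linked AEs, an AE without a matched course absorbs nothing, and two other readings of the same text nearly remove the effect. What is established is an uncapped and under-specified rule whose natural reading errs in the favourable direction and which no planned sensitivity analysis would detect.

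**What to change.** In SAP 6.4 step 3, for merging only, end an SE-linked AE with no resolution date at the stop date of its last linked systemic corticosteroid course if recorded, otherwise at the first scheduled or unscheduled contact after onset. In either case, end it before the onset of the next SE-linked AE whose own steroid course is separated by 1 week or more, or whose course dates are missing, and do not merge across the imputed date in that case. In step 4, state how overlapping AEs are handled. Report the number of SE-linked AEs with imputed resolution dates by year, and keep the as-written rule as a sensitivity analysis, with its reading of the most recent follow-up spelled out. A separate yearly scoring rule is not needed once the end date is capped, and would conflict with step 5.

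The cost is SAP wording and a few lines of code. SAP 4.7 allows an amendment before analysis; the SAP is dated June 2016 and Protocol 16.0 projects completion in December 2019. The documents do not say that course stop dates are held in the medication data, hence the fallback to the next contact. The downside is that a few continuous exacerbations recorded as two AEs may be counted twice, making later-year figures slightly less favourable.
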